5.12. Pharmacokinetic/Pharmacodynamic Analyses

Planned pharmacokinetic and PK/pharmacodynamic (PD) analyses are specified in a separate standalone population based PK/PD analysis plan.

5.13. Safety Analyses

All patients who receive at least one dose of study treatment will be evaluated for safety and toxicity. Adverse event terms and severity grades will be assigned by the investigator using CTCAE, version 4.0.

5.13.1. Extent of Exposure

A summary of drug exposure for study treatment will be presented.

A summary of the dose administration, detailing the number of doses given as planned, reduced, omitted, and delayed will be presented for study treatment. Reasons for dose adjustments will also be summarized.

Dose intensity and relative dose intensity will be summarized for study treatment. Dose intensity is defined as actual cumulative amount of drug taken (mg/m²)/ duration of treatment (week).

5.13.2. Adverse Events

All patients who receive at least one dose of study treatment will be evaluated for safety and toxicity. Adverse event terms and severity grades will be assigned by the investigator using CTCAE v4.0X. In addition, AE verbatim text will also be mapped by the sponsor or designee to corresponding terminology within the Medical Dictionary for Regulatory Activities (MedDRA). Adverse events will be reported using a unified CTCAE/MedDRA reporting process:

- The CTCAE v4.0 term reported by the investigator will be mapped to the MedDRA preferred term (PT) and system organ class (SOC) of the corresponding MedDRA lowest level term (LLT), unless the reported CTCAE term is ‘Other – specify’
- If the reported CTCAE term is ‘Other – specify’ the MedDRA LLT, PT and SOC mapped from the verbatim AE term will be used
- All listings and summaries will use the MedDRA LLT and the MedDRA PT resulting from this process.

A treatment-emergent adverse event (TEAE) is defined as an event that first occurred or worsened in CTCAE grade after the first dose of study treatment. The MedDRA LLT will be used in the treatment-emergent computation.

All observed AEs will be graded using CTCAE version 4.0. Adverse events, deaths and serious adverse events (SAEs) will be listed and summarized. Summaries for patients on therapy will include:

- Summary of all pre-existing conditions and AEs
- Summary of all TEAEs
- Summary of TEAEs possibly related to study treatment
- Summary of all TEAEs by maximum CTCAE grade
- Summary of TEAEs possibly related to study treatment by maximum CTCAE grade
- Summary of deaths on treatment or post-study treatment deaths possibly related to study treatment.

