Relative day within a cycle		Period begins the day after stopping of study treatment and lasts approximately 30 days	Period begins 1 day after short-term follow-up period is completed and continues until death, study withdrawal, or the patient is lost to follow-up	
Procedure Category	Procedure			Comments
Physical Examination	Physical examination (including weight)	X		
	Vital signs	X		Includes blood pressure, pulse, and temperature.
	ECOG performance status	X		
Tumor Assessment	Radiologic imaging according to RECIST 1.1	X		The same method of imaging (CT scan, spiral CT, etc.) used at baseline should be used for each subsequent assessment. Not required if progressive disease is documented while on treatment or if there are clear signs of clinical progression.
	Tumor measurement (palpable or visible)	X		Performed at the same time as radiologic imaging.
Adverse Events Collection/CTCAE Grading		X	X	After Visit 801, only study treatment-related serious events are reported.
Concomitant Medication Notation		X		
Lab/Diagnostic Tests	Hematology	X		
	Chemistry	X		
	ECG	X		
	Exploratory blood sample for biomarkers	X		
	Plasma biomarker sample	X		
	Optional posttreatment biopsy		X	
Health Outcome Measure	Lung Cancer Symptom Scale	X		The LCSS will need to be administered prior to extensive interaction with site personnel.
Follow-Up	Survival Assessment		X	Approximately every 60 (±14) days (telephone assessment is acceptable).

Abbreviations: CT = computed tomography; CTCAE = Common Terminology Criteria for Adverse Events (NCI 2009); ECOG = Eastern Cooperative Oncology Group (Oken et al. 1982); LCSS = Lung Cancer Symptom Scale; RECIST 1.1 = Response Criteria In Solid Tumors Version 1.1 (Eisenhauer et al. 2009).

Table JTJH.2.4. Continued Access Schedule of Activities

	Study Treatment	Follow-Up ^a	
Visit	501-5XX	901	
Procedure ^b			Comments
AE collection	X	X	
Administer LY2606368	X		IV over approximately 60 (+10) minutes once every 14 days.

Abbreviations: AE = adverse event; IV = intravenously.

- a Continued access follow-up begins 1 day after the patient and the investigator agree that the patient will no longer continue treatment in the continued access period and lasts approximately 30 days. No follow-up procedures will be performed for a patient who withdraws informed consent unless he or she has explicitly provided permission and consent.
- b Efficacy assessments will be done at the investigator's discretion based on the standard of care.

3. Introduction

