Several other agents have been shown to have activity in SCLC, and many studies have compared 3-drug regimens to the standard 2-drug regimens with no improvement in efficacy. Topotecan is approved for patients that have ED-SCLC that have failed or relapsed after first line chemotherapy (Demedts et al. 2010). Patients receiving topotecan (1.5 mg/m² daily for 5 days every 21 days) had an overall response rate of 24.3% (von Pawel et al. 1999). The median time to progression was 13.3 weeks and median survival was 25.0 weeks (von Pawel et al. 1999). Adverse events (AEs) associated with this treatment included Grade 4 neutropenia (70.2%), Grade 3/4 anemia (42.3%), Grade 4 thrombocytopenia (28.8%), and documented infection within 2 days of Grade 4 neutropenia (28%) (von Pawel et al. 1999). Other agents, including paclitaxel, irinotecan, vinorelbine, and gemcitabine, have been tested in the second-line setting in an effort to improve on the efficacy and tolerability of topotecan. Despite the modest benefit of topotecan, they have not increased efficacy over topotecan (Chan and Coward 2013), demonstrating the clear need for new agents to improve outcomes for patients with ED-SCLC.

Checkpoint kinase 1 (CHK1), a multifunctional protein kinase, is a regulator of the deoxyribonucleic acid (DNA) damage response (Dai and Grant 2010). CHK1 is a key component of the checkpoint response following DNA damage and is essential for homologous

recombination repair of DNA double strand breaks. It also affects the initiation of DNA replication origin firing, stabilization of replication forks, resolution of replication stress, and coordination of mitosis, even in the absence of exogenous DNA damage (McNeely et al. 2014). Although CHK1 inhibitors previously have been developed as chemopotentiators, given the integral role that CHK1 plays in DNA replication and the regulation of the cell cycle, inhibitors of CHK1 may also have single-agent activity. In particular, replication stress is emerging as a factor that may play a sensitizing role for response to monotherapy with CHK1 inhibitors (Lecona and Fernandez-Capetillo 2014).

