7.7. Concomitant Therapy

No other chemotherapy, immunotherapy, cancer-related hormone therapy, herbal drugs intended to treat cancer, or experimental drugs will be permitted while the patients are on this study. Radiotherapy (including palliative radiotherapy) will only be permitted if it is agreed upon by the both investigator and Lilly. If the lesion that is to be treated is a target lesion, the lesion will be censored at the time of treatment. However, the patient may be eligible to remain on study drug treatment provided there are other lesions that can be followed for progression. Treatment delays of LY2606368 may be required if radiotherapy is administered. In addition, any disease progression requiring other forms of specific antitumor therapy will also necessitate early discontinuation from the study. Replacement hormonal therapy initiated before study entry will be allowed.

Patients should receive full supportive care during the trial. American Society of Clinical Oncology (ASCO) guidelines (Smith et al. 2015) should be followed for patients requiring support with granulocyte-colony stimulating factor (G-CSF). Primary or secondary prophylactic G-CSF support is permitted at the discretion of the investigator. Per the National Comprehensive Cancer Network (NCCN) guidelines, Phase 2 data support the use of pegfilgrastim in regimens with a 2-week cycle, and there is uniform consensus that this is appropriate (Category 2A) (NCCN guidelines for myeloid growth factors [WWW]). As a result, filgrastim, filgrastim biosimilars, or pegfilgrastim may be used.

Prophylactic antibiotics should be considered for use in patients that have experienced neutropenic fever or patients deemed at higher risk for neutropenic fever by the investigators. The treatment should be consistent with ASCO guidelines (Flowers et al. 2013).

Transfusion of packed red blood cells (RBCs) within 14 days of study entry is not permitted. The initiation of erythropoietin therapy to meet eligibility criteria is not permitted. Patients who are stable on erythropoietin for >1 month before study entry may continue their treatment. Erythropoietin and packed RBC transfusion may be used according to ASCO guidelines (Rizzo et al. 2008) if clinically indicated at any time during the study.

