8.1. Discontinuation from Study Treatment

Patients will be discontinued from study treatment in the following circumstances:

- the patient is enrolled in any other clinical trial involving an investigational product or any other type of medical research judged not to be scientifically or medically compatible with this study
- the patient becomes pregnant during the study
- the patient is significantly noncompliant with study procedures and/or treatment
- the patient has evidence of progressive disease
- the patient experiences unacceptable toxicity
- the patient, for any reason, requires treatment with another therapeutic agent that has been demonstrated to be effective for treatment of the study indication. Discontinuation from study treatment will occur prior to introduction of the new agent.
- the investigator decides that the patient should be discontinued from LY2606368
- the patient requests to be discontinued from LY2606368

Patients who are discontinued from LY2606368 will have follow-up procedures performed as shown in the Schedule of Activities (Section 2).

8.1.1. *Discontinuation of Inadvertently Enrolled Patients*

If Lilly or the investigator identifies a patient who did not meet enrollment criteria and was inadvertently enrolled, a discussion must occur between the Lilly CRP and the investigator to determine if the patient may continue in the study. If both agree it is medically appropriate to continue, the investigator must obtain documented approval from the Lilly CRP to allow the inadvertently enrolled patient to continue in the study with or without LY2606368.

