highly effective method of contraception	combined oral contraceptive pill and mini-pill, NuvaRing®, implantable contraceptives, injectable contraceptives (such as Depo-Provera®), intrauterine device (such as Mirena® and ParaGard®), contraceptive patch for women <90 Kg (<198 pounds), total abstinence, or vasectomy.
IB	Investigator's Brochure
IC₅₀	half-maximal inhibitory concentration
ICF	informed consent form
ICH	International Conference on Harmonisation
interim analysis	An interim analysis is an analysis of clinical trial data conducted before the final reporting database is created/locked.
investigational product	A pharmaceutical form of an active ingredient or placebo being tested or used as a reference in a clinical trial.
ITT	intent-to-treat
LCSS	Lung Cancer Symptom Scale
MedDRA	Medical Dictionary for Regulatory Activities
MTD	maximum tolerated dose
open-label	A study in which there are no restrictions on knowledge of treatment allocation, therefore the investigator and the study participants are aware of the drug therapy received during the study.
ORR	overall response rate
OS	overall survival
PD	pharmacodynamics
PFS	progression-free survival

PK	pharmacokinetic
PR	partial response
QTc	corrected QT interval
QTcF	corrected QT interval (Fridericia's formula)
RECIST	Response Evaluation Criteria in Solid Tumors
reporting database	A point-in-time copy of the collection database. The final reporting database is used to produce the analyses and output reports for interim or final analyses of data.
re-screen	to screen a patient who was previously declared a screen failure for the same study
SAE	serious adverse event
SAP	Statistical Analysis Plan
Screen	The act of determining if an individual meets minimum requirements to become part of a pool of potential candidates for participation in a clinical study.
screen failure	patient who does not meet one or more criteria required for participation in a trial
SD	stable disease
SUSARs	Suspected unexpected serious adverse reactions
t_{1/2}	half-life
TEAE: Treatment-emergent adverse event	An untoward medical occurrence that emerges during a defined treatment period, having been absent pretreatment, or worsens relative to the pretreatment state, and does not necessarily have to have a causal relationship with this treatment.
ULN	upper limit of normal
V1	volume of distribution of the central compartment
V2	volume of distribution of the peripheral compartment
V_{ss}	volume of distribution at steady state

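### The SAP's treatment-emergent definition has a start but no end, so next-line toxicity recorded up to Visit 801 enters the all-cause adverse event and laboratory-grade tables

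*SAP*

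**What the plan says.** **Definition.** SAP 5.13.2 counts an event as treatment-emergent if it is "an event that first occurred or worsened in CTCAE grade after the first dose of study treatment". The SAP does not say when the window closes or what happens once other anticancer therapy begins. Protocol Appendix 1 is narrower: "An untoward medical occurrence that emerges during a defined treatment period, having been absent pretreatment, or worsens relative to the pretreatment state". Neither document says when that period ends.

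**Collection.** In Protocol Table JTJH.2.3, short-term follow-up is described as "Period begins the day after stopping of study treatment and lasts approximately 30 days". Adverse events, hematology and chemistry are all scheduled at its visit, Visit 801 (30 ± 5 days). The table adds: "After Visit 801, only study treatment-related serious events are reported".

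**Next therapy.** For a patient who needs another effective agent, Protocol 8.1 says "Discontinuation from study treatment will occur prior to introduction of the new agent". It states no minimum interval. Protocol 10.3.3.4 plans a summary of post-discontinuation anticancer therapies. Protocol 7.7 says that "any disease progression requiring other forms of specific antitumor therapy will also necessitate early discontinuation from the study".

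**Tables.** SAP 5.13.2 summarises all TEAEs and, separately, those possibly related to study treatment, each also by maximum grade. SAP 5.13.4 grades laboratory values by CTCAE and tabulates them in the same style, with no relatedness judgement.

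**The concern.** A patient may stop for progression, start another myelosuppressive regimen within days, and have a nadir on it before Visit 801. Under SAP 5.13.2 that nadir is a TEAE. The Protocol's own background shows why this matters. Section 3.1 reports neutropenia, anemia and thrombocytopenia with topotecan, and Section 3.2.1 reports the same three with LY2606368. The extra events therefore look like the ones this study has to characterise, and with no control arm nothing in an all-cause table sets them apart.

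Characterising safety is a secondary objective, and the all-cause and laboratory rates would be biased upward. The SAP already makes this kind of distinction for deaths: after study treatment, 5.13.2 summarises only those possibly related to it. The all-cause TEAE tables have no equivalent.

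**Working it through.** No figure in the plan depends on this point, so there is none to reproduce. The check is a comparison of passages, followed by an illustration of size.

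**1. Can the overlap occur?**
- The SAP window opens at the first dose and has no stated close.
- Full collection runs to Visit 801. Table JTJH.2.3 has no early close when a new regimen starts. For patients with documented progression it waives only the imaging.
- Protocol 8.1 orders the two treatments (study drug stops first) but sets no gap.
- SAP 5.3 expects follow-up visits to continue after treatment stops and to record later therapy.

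An event caused by the next regimen and recorded by Visit 801 therefore meets the SAP definition.

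**2. Which tables are exposed?**

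| Summary | Filter | Exposed? |
|---|---|---|
| All TEAEs, overall and by maximum grade | None | Yes |
| Possibly related TEAEs, overall and by maximum grade | Investigator attribution, weighing other treatments (Protocol 9.2) | Only if misattributed |
| Derived laboratory grades (SAP 5.13.4) | None | Yes |

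**3. How long is the overlap?** A scan on Days 8–14 of Cycle 3 falls 7–13 days after the Day 1 dose. If the 30 days run from that dose, 30 − 13 = 17 to 30 − 7 = 23 days remain, or 22 to 28 with the +5-day allowance. That is about one 21-day topotecan cycle (Protocol 3.1), before any delay in starting it. Follow-up schedules hematology once, at Visit 801, so a nadir can be missed in the laboratory data.

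**4. Illustration of size, Grade 4 platelets.** Inputs from the documents: 5.7% at the study dose (Protocol 3.2.1), 28.8% with topotecan (Protocol 3.1) and 116 patients (SAP 5.1). Inputs assumed: f, the share of patients starting topotecan-like therapy before Visit 801, and q, the share of its Grade 4 platelet events captured by then. The two risks are treated as independent.

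Rate = 0.057 + f × q × 0.288 × (1 − 0.057)

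- f = 0.1, q = 0.5: 0.057 + 0.0136 = 7.1%, or 116 × 0.0136 = 1.6 extra patients.
- f = 0.2, q = 0.5: 0.057 + 0.0272 = 8.4%, or 3.2 extra patients.
- f = 0.3, q = 0.5: 9.8%. f = 0.5, q = 0.5: 12.5%.
- f = 0.5, q = 1: 19.3%. Full capture is not supported by step 3.

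No comparable sum is offered for the other two toxicities. The 71% Grade 4 neutrophil figure in Protocol 3.2.1 counts only events deemed related, and that section gives no Grade 3/4 anemia rate for the study drug.

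**The case against.** **Collection bounds the window.** A reader might infer that events are counted indefinitely. That is true of the definition but not of the data. After Visit 801 only serious events related to study treatment are reported.

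**A TEAE is not a causal claim.** A reader might infer that next-line toxicity is counted as LY2606368 toxicity. The documents do not support that. Appendix 1 says a TEAE need not be causally related, and related TEAEs have their own tables. This objection stands, and it limits the point to the all-cause and laboratory summaries.

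**Protocol 7.7 may already end collection.** It bars other chemotherapy during the study and ties progression needing other antitumor therapy to leaving the study. Under Protocol 9.2.1, adverse events need not then be actively sought. On that reading most next-line toxicity is never recorded. However, Section 8.2 does not list this reason and still asks for end-of-study procedures, Table JTJH.2.3 continues follow-up, and SAP 5.3 keeps visits going. The conflict is unresolved, so ascertainment after a switch could vary by site.

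**The list in SAP 5.13.2 is headed as covering patients on therapy.** This names who is summarised, not when events stop counting. SAP 5.7 uses the same label for baseline characteristics.

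**All-cause counting to a fixed visit is a defensible, conservative choice.** This stands as an argument against simply cutting events at the switch date. Laboratory values carry no relatedness exception, so a hard cut would discard late LY2606368 effects.

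**Conclusion.** The point holds in a limited form. The SAP's definition lacks an end and a rule for new anticancer therapy, and it does not match Protocol Appendix 1. Next-line toxicity recorded by Visit 801 enters the all-cause TEAE tables and the derived laboratory-grade tables. The related-TEAE tables are protected to the extent that investigators attribute correctly. The response-rate decision and futility rules do not use these tables.

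The size is unknown. The shift from 5.7% to about 7–8% assumes 10–20% switching to topotecan-like therapy and 50% capture, neither of which the documents give. It also assumes that whole-study topotecan rates can be scaled to a short window.

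A reader might also infer that the two cohorts are biased to different degrees. That is possible, but the documents give no switching rate by cohort and plan no between-cohort safety test, so it cannot be asserted.

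**What to change.** 1. In SAP 5.13.2, end the treatment-emergent window at Visit 801, keep later treatment-related serious events, and align the wording with Protocol Appendix 1.
2. Flag adverse events and laboratory values that start or worsen on or after the first post-discontinuation anticancer therapy. Present the all-cause TEAE summaries and the SAP 5.13.4 laboratory-grade summaries both including and excluding them. Keep investigator-related events regardless of date.
3. State how a partial start date for the next therapy is handled for this flag. SAP 5.3 replaces a missing day with the 15th. A true start on the 1st is then moved 14 days late and one on the 31st 16 days early, about half of a 30-day window. A missing month, set to 1 July, can be wrong by far more.
4. Reconcile Protocol 7.7 with Table JTJH.2.3, Section 8.2 and SAP 5.3, so that sites know whether adverse event collection continues after other antitumor therapy begins.

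The cost is a few extra tables, some SAP wording and one date comparison. Protocol 10.3.3.4 and SAP 5.3 already plan to record the later therapy, but its start date has to be captured. Because both versions are shown, no late LY2606368 effect is lost.

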5.13.3. Deaths

All deaths recorded in this study will be included as part of the complete AE listing, where appropriate, and listed separately. A summary of deaths may be presented for all patients on therapy if there are a sufficient number of events for this to be deemed useful.

5.13.4. Clinical Laboratory Evaluation

Laboratory data (hematology, chemistry) will be listed for all patients on therapy. Abnormal results will be listed separately for all patients on therapy.

In addition to the investigator-reported AEs, all relevant hematology and chemistry laboratory values will be graded according to CTCAE version 4.0. These derived values will be included on the listings of laboratory data and summary tables will be produced in a similar manner to those created for the investigator reported AEs.

5.13.5. Vital Signs and Other Physical Findings

All vital signs including blood pressure, pulse, and temperature will be listed for all patients on therapy.

5.13.6. Electrocardiograms

For each patient, single local electrocardiogram (ECG) will be collected according to the study schedule. The ECG data will be summarized and listed.

5.14. Subgroup Analyses

The selected primary and secondary endpoints may be analyzed in the following subgroups:

- Performance status (0 vs. 1)
- Number of prior treatments (2 vs. 3)
- Nature of prior treatments (e.g. cisplatin vs. carboplatin, etoposide/no etoposide, adjuvant radiation/no radiation)

- CNS metastasis (present/absent)
- Geographic region (North America, Europe, Asia)

